From clinical experience, it was observed that many postpartum women with perineal trauma experience several short and long-term physical, physiological, social and psychological postpartum complications such as severe pain, delayed healing of the wound, infection and dyspareunia which may affect the women resumption of function at postpartum period and their future choice of the mode of childbirth. At the same time, there is a lack of statistical documentation on the magnitude of this problem. As well as, there are considerable gaps with implementation of evidence to support management of perineal trauma at postpartum period.

In this context, serious actions should be taken to accelerate the perineal trauma healing and relieve the perineal pain as possible. Most important of these actions is immediate postpartum perineal ice gel pad application, later performance of pelvic floor exercises (Kegel exercises) and perineal warm compresses. These interventions have a lot of advantages as they are not costing, appropriate to postpartum women in many situations, and

safe. Moreover, these interventions promote, accelerate the healing, decrease the perineal pain and facilitate restoration of muscle tone (Farrag, Eswi, & Badran, 2016).

In Egypt, there is a scarce of RCT studies that was conducted in this respect and they have contradicting results. Moreover, almost all these studies were conducted to test only one intervention or compare between two interventions for treatment of perineal trauma but no study tested the impact of a designed protocol of care which starts from immediate postpartum and continues throughout the first week where a combination of therapies is implemented. So, the results of this study will add to the quality of evidence on the effectiveness of postpartum interventions for improving the recovery of postpartum perineal trauma. This protocol may be used as guidelines to be implemented for better quality of patient care.

Aim of the study

The aim of the current study is to test the effect of designed protocol of care on the outcomes of postpartum perineal trauma.

Outcome measures

- **Primary outcomes:** Severity of perineal pain, delayed perineal trauma healing.
- **Secondary outcomes:** Occurrence of infection, postpartum difficulty with turning/rolling in bed, getting out of bed, sitting, walking, defecation and urination.

Research Hypotheses

To fulfill the aim of this study the following research hypothesis is formulated:

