Operational definition of terms

1- A designed protocol of care for postpartum perineal trauma: It is a protocol developed by the investigator based on systematic reviewed studies and randomized controlled trials. The protocol entails a combination of 3 evidence-based therapies for postpartum perineal trauma; application of perineal ice gel pad, pelvic floor exercises (Kegel exercises) and perineal warm compresses applied in steps starting from immediate postpartum and continues throughout the first week in order to relief immediate and sustained perineal trauma.

2- Perineal trauma: Is any injury to the perineum during childbirth which occurs spontaneously (1st or second degree tear) or intentionally through a surgical incision (episiotomy).

3- Postpartum perineal trauma outcomes: It include the following outcomes:

- a- Postpartum perineal pain: It will be assessed by Visual Analogue Scale for pain intensity (VAS).
- b- Postpartum perineal trauma healing: It will be assessed by standardized REEDA scale.
- c- Postpartum perineal trauma infection: It will be assessed by standardized REEDA scale.
- d- Postpartum difficulty with performing functional activities: It refers to postpartum difficulty with turning/ rolling in bed, getting out of bed, sitting, walking, defecation and urination. It will be assessed by Visual Analogue Scale (VAS) for rating functional activities.

Subjects and Methods

Research Design

A randomized controlled trial will be used to fulfill the aim of proposed study. The randomized control trial (RCT) is a trial in which subjects are randomly assigned to one of two groups: one (the experimental group) receiving the intervention that is being tested, and the other (the comparison group or control) receiving an alternative treatment (Spieth et al, 2016).

Sample

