Tool (B) Visual Analogue Scale for Pain Intensity (VAS): It is a standardized linear scale developed by Freyd et al., (1923). It is a self-reported 10 cm horizontal line which represents the subjective estimation of pain intensity. It comprises 0-10-point numerical scale, the two opposite ends representing no pain to severe pain as follows: no pain (0), mild pain (< 4), moderate pain (4 - <8), and sever pain (8-10). This tool is valid and reliable, test-retest reliability coefficient of the VAS has been demonstrated in several studies as $r =0.62$ (Derya, Ergul, Senol, &Aslan, 2017).

Tool (C) Visual Analogue Scale (VAS) for rating functional activities: This tool is adopted from Karakaya et al.,(2012), the difficulty with performing functional activities as (turning/ rolling in bed, getting out of bed, walking, sitting, defecation and urination) will be evaluated by using horizontal 10 cm visual analogue scale for each functional activity, the scale will be applied six times to measure the difficulty with each activity (VAS will be

marked by the women). The scoring for each activity will be as follows: no difficulty (0), mild difficulty (< 4), moderate difficulty (4 - <8), and sever difficulty (8-10). The total score will be recorded (0-60 point), the lowest score (0) indicate no difficulties and the maximum score (60) indicate maximum difficulty. The total score will be interpreted as the following no difficulties (0), Mild difficulties (1 - < 24), Moderate difficulties (24 - < 48), Sever difficulties (48-60). This tool is valid and reliable, test-retest reliability coefficient has been demonstrated as $r = 0.82$ (Karakaya et al., 2012).

Tool (D) Standardized REEDA Scale: This tool is adopted from Davidson (1974), REEDA scale will be used to assess condition of perineal trauma. REEDA scale is a descriptive scale having a four point categorical score (0-3) that measures five components associated with the healing process of perineal trauma. This includes: Redness, Edema, Ecchymosis, Discharge and Approximation of sutures. The total score ranged from 0 to 15 and categorized as the following; 0 to 2 cm good wound healing with no infection, 3 to 5 cm moderate wound healing, 6 to 8 cm mild wound healing, and 9 to 15 cm poor wound healing with infection . This tool is valid and reliable, test-retest reliability coefficient of the REEDA scale has been demonstrated as $r = 0.70$ (Farrag, Eswi, & Badran, 2016).

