Tool (E) Postpartum Follow up Sheet: This tool will be designed by the researcher after reviewing the related literature and will be revised by experts in gynecology and maternity nursing department and will include items to assess mother compliance with ice gel pad application through the first 24 hours and assess women's need for additional analgesia. Also, assess the women compliance with Kegel exercise performance from six hours postpartum till one week and compliance with the application of warm compresses per day from 48 hours postpartum till one week.

A designed Protocol of Care for Postpartum Perineal Trauma: It is a protocol developed by the investigator based on systematic reviewed studies done by (East; Begg; Henshall; Marchant; & Wallace (2009); Shahrahmani et al,(2016); East; Dorward; Whale;& Liu, (2020); Kridsana; Kunyanut; & Thitiporn (2020); and several studies as a quasi experimental time series study by Farrag, Eswi, & Badran,(2016); a randomized controlled trial by Derya, Ergul, Senol, & Aslan, (2017); and a quasi experimental study by Khosla & Pratibha, (2017); a quasi experimental study by Yuliani, Rizka,(2019).

The protocol entails a combination of evidence-based therapies for postpartum perineal trauma that is applied in steps starting from immediate postpartum and continues throughout the first week in order to relieve immediate and sustained perineal trauma.

Description of the protocol:

1. Application of perineal ice gel pad: Immediately postpartum (within 30 minutes to one hour) and through the first 24 hours postpartum to help reduce perineal pain, edema and stimulate repair process.
2. Postpartum performance of pelvic floor exercises (Kegel exercises): After six hours till one week postpartum to accelerate healing of perineal trauma and for further reduction of sustained perineal pain.
3. Postpartum perineal warm compresses: After 48 hours till one week postpartum to promote better healing of perineal trauma, prevent complications, prevent infection and further reduction of sustained perineal pain.

Ethical consideration

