Initial Assessment: Initial assessment for women in both groups (study & control group) will be carried out in relation to body mass index (BMI), type of perineal trauma after delivery (episiotomy, or tears), degree of perineal tear (1st or 2nd degree tear), and assessment of perineal trauma condition will be done using standardized REEDA scale . Also, women will be asked to indicate the degree of perineal pain using Visual Analogue Scale for pain intensity (VAS).This assessment will take 15 minutes for each woman.

Intervention:

Intervention for the study group: For the study group the intervention will be according to a designed protocol of care that entails; 1) Application of ice gel pad on perineal trauma for the first 24 hours post partum; 2) Performance of pelvic floor exercises (Kegel exercises) from six hours till one week postpartum; 3) Application of warm compresses after 48 hours and through the first week postpartum. The investigator will perform demonstration and then redemonstration by the women on each intervention will be done. A designed booklet (developed previously) that explains each intervention will be given to each woman.

Immediately after delivery (within 30 minutes to one hour after delivery), an ice gel pad will be applied to perineal trauma. It will be available in an individual package(every woman will alternate between two ice gel pads); each gel pad will have fixed standardized diameter (an approximately 5 cm width, 23 cm length, and 1.5 cm thickness) and approved by Egyptian ministry of health. It will be kept in the freezer for 45–60 minutes and

will be removed when frozen. Then, it will be wrapped in a sterile pad and applied to cover the perineum and anal region. The pad will be compatible with the anatomical structure of the perineum.

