For control group follow up by telephone call will be done at 24 hours to assess degree of perineal pain using Visual Analogue Scale for pain intensity (VAS), the women's need for additional analgesia and assess women's postpartum difficulty with functional activities as turning/ rolling in bed, getting out of bed, sitting, walking, defecation and urination using Visual Analogue Scale (VAS) for rating functional activities. Also, telephone follow up will be done at third and fifth day postpartum to assess degree of perineal pain using Visual Analogue Scale for pain intensity (VAS) and assess women's postpartum difficulty with performing functional activities as turning/ rolling in bed, getting out of bed, sitting, walking, defecation and urination using Visual Analogue Scale (VAS) for rating functional activities.

Then, a final postpartum follow up visit for both groups at the seventh day will be conducted for assessment of perineal trauma condition and healing process using

standardized REEDA scale and assess the degree of perineal pain using Visual Analogue Scale for pain intensity (VAS).

References

Davidson, N. (1974). REEDA: evaluating postpartum healing. *J Nurse Midwifery*. 1974; 9:6–9.

Derya, K., Ergul, Senol, &Aslan, E. (2017). The Effects of Cold Application to the Perineum on Pain Relief After Vaginal Birth, *Asian Nursing Research*, Volume 11, Issue 4, Pages 276-282, ISSN 1976-1317.

El-Saidy, T. M. K., Abou shady, R. M. N., &Soliman, H. F. A. (2018). Effect of Applying Crushed Ice Gel Pads on Episiotomy Pain and Wound Healing Among Postpartum Primiparous Women. *ijnd* 2018, 8, 19-29.

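### Infection is examined only by REEDA, at the initial assessment, about six hours and day 7, so the plan measures infection present on day 7 rather than infection occurring during the week

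*Combined protocol and SAP*

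**What the plan says.** Under Outcome measures, infection comes first among the secondary outcomes: "Occurrence of infection, postpartum difficulty with turning/rolling in bed". No time point or period is attached to it. Operational definition of terms names one instrument: "Postpartum perineal trauma infection: It will be assessed by standardized REEDA scale".

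The REEDA bands are under Tools for Data collection, Tool D. A total in the lowest band means "0 to 2 cm good wound healing with no infection"; a total in the highest means "9 to 15 cm poor wound healing with infection". The two middle bands, 3 to 5 and 6 to 8, grade healing and say nothing about infection.

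REEDA is scored three times under Procedure. In the initial assessment of both groups, "assessment of perineal trauma condition will be done using standardized REEDA scale". It is repeated six hours after the ice gel pad is applied (study group) or six hours after delivery (control group). The third time is day 7, when "a final postpartum follow up visit for both groups at the seventh day will be conducted for assessment of perineal trauma condition".

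Preventing infection is a stated aim. Description of the protocol says the warm compresses, used from 48 hours to one week, are meant among other things to "prevent complications, prevent infection and further reduction of sustained perineal pain".

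**The concern.** Occurrence normally means that an event happened at some time in a period, here the first postpartum week. A REEDA total describes the wound at the moment it is inspected. The first two inspections fall within hours of birth, so for infection that develops later there is one look, on day 7.

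Three calls lie between the second and third inspections. If none asks about the wound or its treatment, an infection that came and went leaves no trace. Two results are affected. The infection count would omit such cases. The day-7 healing score, which measures a primary outcome, could also reflect treatment received outside the trial that nobody recorded. The component intended partly to prevent infection runs from 48 hours to day 7, and infection is examined only at the end of that period.

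**Working it through.** The plan states no infection rate or expected count, so there is no figure to reproduce. The check sets each planned contact against what it is described as collecting.

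| Contact | Described content | Infection information |
|---|---|---|
| Initial assessment, both arms | REEDA, pain VAS, BMI, trauma type and degree | REEDA, but before later infection could appear |
| About 6 h, both arms | REEDA, pain VAS | REEDA, same limit |
| 24 h call | Pain, function, analgesia need; pad compliance (study arm) | None described |
| Day 3 and day 5 calls | Pain, function; compliance with exercises and compresses (study arm) | None described |
| Day 7 visit, both arms | REEDA, pain VAS | REEDA total that day; no history described |

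Tool E is described as covering compliance and the need for additional analgesia only.

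**Interval between inspections.** Day 7 is 7 × 24 = 168 h. In the control arm the second REEDA is at 6 h, leaving 168 − 6 = 162 h. In the study arm the pad goes on 30 to 60 minutes after delivery, so the second REEDA is at 6.5 to 7 h, leaving 161 to 161.5 h.

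**What the bands do with an infection arising in that interval.**
- Day-7 total 9 to 15: counted as infection.
- Day-7 total 3 to 8: no infection label; the plan does not say how it is coded.
- Day-7 total 0 to 2: labelled as no infection.

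Only the second and third cases are lost, and only the third is positively recorded as uninfected.

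**Illustration under assumed rates.** None of these rates is in the documents. Let p be the true seven-day infection proportion in an arm of 50, and c the fraction of cases still scoring 9 or more on day 7, taken as equal in both arms. Expected counted cases are 50 × p × c, and the observed risk difference is c times the true one. The last four columns give exact power of Fisher's test, two-sided 0.05, 50 per arm. Fisher's test is used throughout for simplicity; the Statistical plan reserves an exact test for expected frequencies below 5.

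| Assumed p, control vs study | Expected cases at c = 1 | c = 1 | c = 0.75 | c = 0.50 | c = 0.25 |
|---|---|---|---|---|---|
| 10% vs 2% | 5 vs 1 | 0.19 | 0.09 | 0.02 | 0.001 |
| 20% vs 5% | 10 vs 2.5 | 0.51 | 0.34 | 0.16 | 0.02 |
| 30% vs 10% | 15 vs 5 | 0.64 | 0.45 | 0.24 | 0.06 |

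With equal c the risk ratio is unchanged and information is lost. With unequal c the observed ratio is the true ratio multiplied by c(study)/c(control), a factor the planned data cannot estimate.

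**The case against.** The best defence is that the plan defines infection operationally through an inspection scale and sets no window, so a day-7 finding may be all that was meant. Contact times are the same in both arms, so the gap is symmetric by design. Infection is one secondary outcome, is in neither sub-hypothesis, and is not named in the Statistical plan. The illustration also shows weak power even with full capture (0.19 to 0.64), so better ascertainment would mainly improve description. Tool E is described only in outline and may yet hold more. All of this limits the importance of the point. None of it supplies the missing information or makes a day-7 finding a measure of occurrence.

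Four stronger readings are tempting, and the documents do not support them.
- A reader might infer that any infection treated before day 7 is recorded as uninfected with good healing. That needs a total of 0 to 2; totals of 3 to 8 carry no infection label, and 9 to 15 is still counted.
- The gap is about 96% of the week (161/168), and a reader might infer that most infections are missed. Hours between inspections do not measure missed events, because an infection that persists is seen on day 7.
- A reader might put a number on the loss. For example, 4 to 10% of 50 is 2 to 5 cases per arm, and losing one third to one half gives 0.7 to 2.5. Neither the rate nor the fraction comes from the documents.
- A reader might infer bias between arms because only the study arm gets a booklet and teaching sessions. The booklet is said to explain the interventions; nothing says it covers signs of infection or when to seek care. A difference is possible but not shown.

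**Conclusion.** The point stands as a mismatch between the outcome's name and its measurement. As described, the plan captures REEDA-defined infection present on day 7. Infection that arises after about six hours and falls below a total of 9 by day 7 is not captured as infection, and treatment that may have improved the day-7 healing score is not recorded. The number of missed cases and any imbalance between arms are unknown, because the documents give no infection rate, resolution time or treatment frequency. The conclusion assumes that the calls and Tool E collect what they are described as collecting and no more. It is a worthwhile, inexpensive improvement to a secondary outcome and to the interpretation of the healing score; it does not show that the primary comparison is biased.

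**What to change.** At the 24-hour, day-3 and day-5 calls and the day-7 visit, ask both arms the same fixed questions and enter the answers on Tool E:

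- new wound discharge, wound opening or fever since the last contact;
- wound infection diagnosed, or an antibiotic prescribed for the wound, with the date;
- an unscheduled visit or readmission for the wound.

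Name the examined outcome *REEDA-defined infection at day 7*. Report by arm, separately and in combination with it, wound infection diagnosed or treated from delivery to day 7. Present day-7 REEDA with the number of women treated for wound infection in each arm.

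The cost is about a minute per contact already scheduled and a few lines on Tool E. The downside is that the added events are self-reported and no blinding is described, so reporting could differ by arm. They should therefore be shown apart from the examined outcome and not replace it.

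The Statistical plan is written in the past tense. If data collection is complete, rename the outcome as above and state that infections no longer scoring 9 or more by day 7, and treatment for them, were not ascertained.

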Data were statistically described in terms of mean \pm standard deviation (\pm SD), or frequencies (number of cases) and percentages when appropriate. Because the groups are large enough, comparison of numerical variables between the study groups was done using a student t test for independent samples (including statistical analysis of the primary outcomes as perineal pain scores and perineal trauma healing scores among the study and control groups). For comparing categorical data, the chi-square test was performed (including statistical analysis of the difficulties with functional activities; secondary outcome). An exact test was used when the expected frequency was less than 5. Two sided p values less than 0.05 were considered statistically significant. All statistical calculations were done using the computer programme IBM SPSS (Statistical Package for the Social Sciences; IBM Corp., Armonk, NY, USA), release 22 for Microsoft Windows.

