A total of (100) postpartum women with normal spontaneous vaginal delivery and having postpartum perineal trauma will be recruited for this study and randomly assigned to either study group (50) women or control group (50) women. Inclusion criteria will be according to the following; primiparous or 2nd. multiparaous women with postpartum perineal trauma either episiotomy or perineal tear (first and second degree only), age not exceeding 40 years, , body mass index (BMI)within normal 18.5-24.9 kg/m² or overweight 25-29.9 kg/m², free from any high risk condition affecting perineal trauma healing (e.g., diabetes mellitus or obesity), over 37 week gestation and not having any complications during labor and delivery(e.g., abnormal presentation, obstructed labor or delivered with instrument), not having any immediate postnatal complications such as postpartum hemorrhage.

The sample size was calculated using a G-power version 3.1.1 for power analysis. A Power of .95 ($\beta = 1 - .95 = .05$) at alpha .05 (one-sided) was used as the significance level, and effect size= (80%).

Setting

The study will be conducted at postpartum ward of emergency department for labor and delivery in Obstetrics and Gynecology Hospital at Kasr El Aini University Hospital affiliated to Cairo University. Postpartum ward provides care for postpartum women with normal vaginal delivery and post abortion women. The capacity of the ward is 20 beds which provide care for approximately (3000) normal deliveries annually according to local statistics for the year 2020 (Kasr El Aini University Hospital Statistics, 2020).

Tools for Data collection

Required data will be collected by using 5 tools: A) Structured interview schedule; B) Visual Analogue Scale for pain intensity(VAS); C) Visual Analogue Scale (VAS) for rating functional activities; D) Standardized REEDA scale; and E) Postpartum follow up sheet.

Tool (A) Structured Interview Schedule: This tool will be designed by the investigator and will include two sections:

- The first section: Will include four items to assess participants' demographic data such as (age, BMI, educational level, occupation, residence).
- The second section: Will include four items to assess the participants current obstetric history (e.g., obstetric code), type of perineal trauma after delivery (episiotomy, or tears) and degree of perineal tear (1st or 2nd degree tear).

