The primary official permission will be obtained from the research ethics committee of faculty of nursing, Cairo University to approve the tools and the study. Also, the investigator will explain to the women the purpose and nature of the study and its importance. In addition, informed written consents will be obtained from women who were willing to participate in the study after ensuring that their participation is voluntary and the trial posed no risk or hazards on them. As well, each woman will be assured that she has the right to withdraw of the trial at any time without any effect on her care. Then, confidentiality will be assured through coding of data by the investigator and keeping the data in a secret place.

Validity and reliability

Un standardized tools were submitted to 3 experts in the field of maternity nursing to test content validity, clarity of sentences and an appropriateness of content. Modifications were carried out according to the expert judgment.

Procedure

First, the primary official permission will be obtained from the research ethics committee of faculty of nursing, Cairo University to approve the tools and the study. An official permission will be granted from the hospital administrative personnel in the recommended setting to collect the data. Then, data collection will be carried out through five steps in each group: Recruitment & randomization; interviewing; initial assessment; intervention; follow up and monitoring.

Recruitment and Randomization of sample: Women who will meet the eligibility criteria will be recruited from a written list done by the investigator every day. Those plotted in the odd number will be selected until completion of the sample. Random assignment of the subjects into two groups will be done through an opaque sealed envelope reflecting the type of each group, and then the eligible women will be asked to choose an envelope to

determine their groups.

Interviewing: During interview the aim of study will be explained to the women in both groups (study & control group) to gain their acceptance to participate in the study then data related to socio-demographic status and obstetric history will be collected from both groups

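### Both primary scores are compared by unadjusted t test although baseline VAS, REEDA and trauma type are recorded; the test is valid, but a prespecified ANCOVA would usually be more precise.

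*Combined protocol and SAP*

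**What the plan says.** - **Analysis.** In the Statistical plan, "comparison of numerical variables between the study groups was done using a student t test for independent samples". The same sentence names the pain and healing scores as covered. No covariate, change score, ANCOVA, mixed model or stratified analysis appears anywhere.
- **Baseline data.** Under Initial Assessment, trauma type and tear degree are recorded in both groups, women rate their pain on the VAS, and "assessment of perineal trauma condition will be done using standardized REEDA scale".
- **Allocation.** Under Recruitment and Randomization of sample, "eligible women will be asked to choose an envelope". No stratification is described, although the Sample section admits episiotomies, first-degree tears and second-degree tears together.
- **Order of steps.** The Procedure section lists them as "Recruitment & randomization; interviewing; initial assessment; intervention; follow up and monitoring". No blinding of women or assessor is described.
- **Time points.** Under Intervention and Follow up and monitoring, VAS is taken at 6 hours, 24 hours and days 3, 5 and 7, and REEDA at 6 hours and day 7. None is named as primary.

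**The concern.** The trial collects the variables most likely to predict its two primary scores and then leaves them out of the comparison. Over all possible randomisations the t test is unbiased and keeps its 5% error rate. What is lost is precision, and in the one trial actually run any chance baseline difference stays in the estimate. If such a difference is seen and no covariates were fixed beforehand, the sponsor must either leave it in or adjust after the fact, which readers can fairly question.

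The order of steps limits the remedy. A self-reported VAS and an investigator-rated REEDA taken after the envelope is opened could be influenced by knowledge of the group, and adjusting for an influenced baseline could introduce bias. Trauma type and tear degree are fixed at delivery and do not carry this risk.

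**Working it through.** **Inputs from the documents.** 50 women per group (Sample); power 0.95, one-sided alpha 0.05 and an effect size of 80% (Sample); two-sided 0.05 at analysis (Statistical plan); test-retest reliability 0.62 for VAS (Tool B) and 0.70 for REEDA (Tool D).

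**Assumptions.** The 80% is read as d = 0.8. The correlation r between baseline and outcome is not given, so it is varied from 0.1 to 0.7. The reliabilities are taken as rough ceilings for r, about 0.6 for VAS and 0.7 for REEDA. In the r table, trauma type is assumed to explain nothing.

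**The plan's own figure.** With d = 0.8, alpha 0.05 and power 0.95, the noncentral t calculation gives 35 per group (70) one-sided and 42 per group (84) two-sided. The stated 100 is not reproduced, but nothing below depends on that. At 50 per group, two-sided power is 97.7%.

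**Effect on the standard error.** In outcome-SD units the t test has SE = sqrt(2/50) = 0.2 and a 95% half-width of 1.984 × 0.2 = 0.397. ANCOVA multiplies the SE by sqrt(1 − r²) before any cost. The baseline score (one term) and three-level trauma type (two terms) give q = 3, and the average net factor is sqrt((1 − r²)(N − 3)/(N − q − 3)) = sqrt((1 − r²) × 97/94). Residual degrees of freedom fall from 98 to 95. Power uses the noncentral t with noncentrality 5d divided by the net factor.

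| r | Gross fall in SE | Net change in SE | 95% half-width (SD) | Power, d = 0.8 | Power, d = 0.5 (assumed) |
|---|---|---|---|---|---|
| t test | – | – | 0.397 | 97.7% | 69.7% |
| 0.1 | 0.5% | +1.1% | 0.401 | 97.5% | 68.7% |
| 0.2 | 2.0% | −0.5% | 0.395 | 97.8% | 70.1% |
| 0.3 | 4.6% | −3.1% | 0.385 | 98.3% | 72.4% |
| 0.5 | 13.4% | −12.0% | 0.349 | 99.5% | 80.3% |
| 0.6 | 20.0% | −18.7% | 0.323 | 99.8% | 86.1% |
| 0.7 (REEDA only) | 28.6% | −27.5% | 0.288 | >99.9% | 92.7% |

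Break-even is r = sqrt(1 − 94/97) = 0.176. The worst case, r = 0, is sqrt(97/94) = 1.016, a 1.6% loss. With the baseline score alone (q = 1), break-even drops to sqrt(1/97) = 0.10.

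**Simulation check.** With 20,000 simulated trials per setting from r = 0.1 to 0.6 and the same three terms, the interval width changed by +1.1%, −0.4%, −3.1%, −12.0% and −18.7%. A separate simulation with one covariate gave type I error of 0.047 to 0.052 for the t test and 0.048 to 0.050 for ANCOVA.

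**Chance imbalance.** The baseline difference between groups has SD sqrt(2/50) = 0.2 in baseline-SD units. A difference above 0.3 SD therefore occurs with probability 2(1 − Φ(1.5)) = 0.134. It shifts the unadjusted estimate by r × 0.3, which is 0.03 SD at r = 0.1 and 0.18 SD at r = 0.6.

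**Trauma type only** (q = 2, factor sqrt((1 − R²) × 97/95)). At an assumed R² of 1%, 5% and 10%, the SE changes by +0.5%, −1.5% and −4.1%.

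**The case against.** The strongest reply is that nothing is wrong: the t test is valid, and at d = 0.8 power is 97.7% against 97.5% to 99.8% for ANCOVA with r up to 0.6, so no conclusion at the planned effect depends on the choice. This stands, and it is why the point is an improvement and not a fault.

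A second reply is that the larger gains are not available as the plan is written. With allocation known before baseline scoring, only trauma type and degree are free of risk, and that adjustment runs from a 0.5% loss to a 4.1% gain. This also stands, and the fix carries the condition. Strictly, a baseline uninfluenced by allocation would be enough, but the documents describe no safeguard of that.

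Third, r is unknown. Baseline is taken around the first hour after delivery, and a correlation with a day-7 score could be low. This cannot be excluded, but the loss is bounded at about 1.6%.

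Fourth, narrower intervals and protection against imbalance are one gain. The unadjusted variance of 0.04 splits into 0.04(1 − r²), which ANCOVA keeps, and 0.04r², which is the imbalance part. This is correct; the 13% figure is the same benefit seen within a single trial and should not be added to it.

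Finally, the Statistical plan is written in the past tense. If outcome data have already been seen, an ANCOVA can no longer be called prespecified.

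**Conclusion.** The point holds as a low-cost improvement. The planned t test is valid, but it ignores baseline data that the trial already collects. With the full three-term model, the net change in standard error runs from a 1.6% loss at r = 0 to a gain of 12.0% at r = 0.5 and 18.7% at r = 0.6, with break-even near 0.18. At the planned effect the power gain is negligible. At an assumed d = 0.5, power would rise from 69.7% to 80.3% if r were 0.5. These sizes rest on an r that the documents do not supply, on roughly normal scores, and on a baseline unaffected by allocation. Under the order of steps now written, only the trauma-type adjustment can be relied on, and its effect is small.

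**What to change.** 1. In the Statistical plan, make the primary analysis of each score an ANCOVA on group, the baseline value of the same score, and trauma type (episiotomy, first-degree tear, second-degree tear). Report the adjusted mean difference with its 95% CI and keep the t test as a sensitivity analysis.
2. Name the time point to which this applies. Day 7 is one candidate, as the only follow-up visit and a time when both scores are taken. The choice is the sponsor's.
3. In the Procedure section, place the initial assessment before the envelope is opened. If the order is not changed, adjust only for trauma type and degree.
4. Fix the covariates before outcome data are seen. If that is no longer possible, present the ANCOVA as a supportive analysis and say so.

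The cost is a few sentences, a change in the order of two existing steps (the assessment is planned to take 15 minutes), three residual degrees of freedom, and a slight loss of precision if r is below about 0.18. No new measurement or software is needed.
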